14.2.1 Primary estimand

The primary estimand is the rate of moderate to severe acute exacerbations of AECOPD in adults with a primary clinical diagnosis of COPD and will be measured as the rate per person per year. The estimand will follow the principal stratum strategy and those who will be randomised and then receive a positive or indeterminate result in their IGRA test will be excluded from all analyses.

The primary estimand can be summarised as follows:

Population: Adults with a primary clinical diagnosis of COPD and a negative IGRA test, ≥2 AECOPD in the last 12 months, who have not been Immunosuppressed and have not received >20mg prednisolone per day for >14 days in the last 3 months, have not previously experienced of allergic reaction to vaccine and are not pregnant, if they are female.

Treatment Conditions: BCG vaccine compared to no vaccine (see Section 7.1 for details on the intervention)

Outcome: Rate per person per year of moderate to severe acute exacerbations of AECOPD

Time: 12 months after randomisation in the no vaccine group and 12 months after receiving the BCG vaccine in the BCG group

Summary Measure: Adjusted incidence rate ratio and 95% confidence interval

Intercurrent Events and Strategies: The intercurrent events are: positive or indeterminate IGRA test; treatment non-receivers (those who randomised to receive but did not receive the BCG vaccine for any reason); withdraw consent for providing follow up data or lost to follow up; and death. All intercurrent events apart the first one (i.e. tested positive in their IGRA test) will be dealt with using the treatment policy strategy for the primary estimand as we want to evaluate the treatment effect as it would occur in normal practice. The intercurrent event, positive or indeterminate IGRA test will be dealt with using the principal stratum strategy because we are interested in the treatment effect in the principal stratum in which the intercurrent event would not occur.

Other strategies evaluating different estimands will be discussed in further detail in the SAP.

Rate of moderate to severe acute exacerbations of AECOPD will be analysed using a negativebinomial regression model, incorporating exposure time (person-years) and adjusting for the minimisation variables listed in Section 6.6 to estimate the adjusted incidence rate ratio and 95% confidence interval. The two-sided p-value relating to the intervention group parameter as generated by the model will be presented.

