All patients will be asked to provide a blood sample (used to perform the IGRA test), DBS sample, a sputum sample and complete a nasopharyngeal (nose and throat) swab (if they produce in the stable state). Participants will also be taught how to obtain their own DBS sample by a medically qualified member of staff as they will be asked to complete this at home at the specified follow up time points. A patient interviewer-administered questionnaire will be used to collect quality of life (CAT score) and exacerbation management in the last 12 months.

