6.6 Randomisation method

Participants will be randomised at the level of the individual in a 1:1 ratio to either BCG vaccine or no vaccine via a central secure web-based EDC system. A minimisation algorithm will be used within the randomisation process to ensure balance in the BCG vaccine allocations over the following variables:

- Age (<65 or ≥65 years)
- Prior BCG vaccination or TB infection (yes/no)
- Consent to participate in the detailed mechanistic sub-study (yes/no)
- Site

To avoid the possibility of the intervention allocation becoming predictable, a random element will be included in the algorithm. Full details of the randomisation specification will be stored in a confidential document at BCTU.

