9.8 Schedule of assessments

Event	Baseline	IGRA test	Vaccine administered ¹	1 month +/-7 days ²	3 months +/- 14 days ²	12 months +/- 1 month ²
Eligibility check	X					
Consent	X					
IGRA test	X	X ³				
Demographics	X					
Medical history (including vaccine history)	x					х
Smoking status	X					Х
Medications	X					Х
Spirometry (FEV1/FVC)	X					
CAT score	X				X	Х
Randomisation	X					
IGRA test results		Х				
Pregnancy test (if applicable)			x			
BCG			X			
Exacerbation rate/symptoms/treatment	x				X	х
DBS (all participants)	X				X	Х
Sputum sample	X				Х	
Throat/nose swab	X				Х	
DBS (exacerbation sampling)					Х	

Table 2: Schedule of Assessments

STABILISE Protocol

Venepuncture	Х		X4	X4	X ⁴
Follow up questionnaire				Х	X
Adverse events				Х	Х

¹ The vaccine, where allocated, should be administered to the participant within 6 weeks of randomisation.

²Follow up dates will be calculated using the date that the treatment was administered on for those allocated to the intervention arm and the date of randomisation for those allocated to the control arm.

³Further test required if result of first test is indeterminate

⁴*Mechanistic subgroup only*

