14.2 Analysis outcome

A separate Statistical Analysis Plan will be produced and will provide a more comprehensive description of the planned statistical analyses. A brief outline of the planned analyses is given below. The primary comparison groups will be composed of those randomised to BCG vaccine versus those randomised to the control arm. In the first instance, all analyses will be based on the intention to treat principle, i.e., all participants will be analysed in the intervention group to which they were

randomised irrespective of adherence to randomised intervention or protocol deviations. For all outcomes, appropriate summary statistics and differences between groups, e.g., incidence rate ratios, mean differences, relative risks, absolute differences will be presented, with 95% confidence intervals and p-values from two-sided tests also provided. Where possible intervention effects will be adjusted for the minimisation variables listed in Section ENROLMENT and RANDOMISATION , and baseline values (where appropriate and available). No adjustment for multiple comparisons will be made.

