14.2.3 Secondary outcome estimands

Estimands for the secondary outcomes will deal with intercurrent events as per the primary estimand. All analysis models will adjust for the minimisation variables listed in Section 6.6. The differences between groups for the secondary outcomes will be presented along with 95% confidence intervals. Incidence rate outcomes (e.g. the hospitalisation rate for infective exacerbation

of airways disease at 12 months) will be analysed as per the primary outcome using negativebinomial regression models incorporating exposure time (person-years). Count outcomes (e.g. total number of days of antibiotics for AECOPD, total number of days of oral steroid therapy for AECPOD) will be analysed using Poisson regression models to calculate adjusted incidence rate ratios, unless there is compelling evidence of overdispersion, in which case negative-binomial regression models will be used. The chosen model will incorporate exposure time (person-years). The continuous secondary QOL outcome (using the CAT score) will be analysed using mixed effects linear regression models to calculate an adjusted mean difference accounting for the collection of QOL at multiple time points. Ordinal outcomes (e.g. type of exacerbation classified using two different approaches: i) a three-level classification based on Anthonisen criteria, and ii) a four-level classification based on clinical adjudication) will be analysed using mixed effect ordinal regression models to estimate the adjusted odds ratios.

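### The protocol leaves open whether the prior-year exacerbation count enters the primary model; naming it would be a modest, nearly free gain in precision

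*Protocol*

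**What the plan says.** Protocol section 14.2.1 defines the primary analysis as a negative binomial regression with person-years of exposure, "adjusting for the minimisation variables listed in Section 6.6 to estimate the adjusted incidence rate ratio". Section 14.2.3 sets the rule for the secondary outcomes: "All analysis models will adjust for the minimisation variables listed in Section 6.6". Section 6.6 lists four such variables: age below or from 65, "Prior BCG vaccination or TB infection (yes/no"), consent to the mechanistic sub-study, and site.

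The opening of section 14.2, which covers all outcomes, is wider. It says that effects will where possible be adjusted for the minimisation variables "and baseline values (where appropriate and available"), and it leaves the fuller description to the SAP.

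Exacerbation history is a baseline item for everyone. Section 6.2 describes an interviewer-administered questionnaire "to collect quality of life (CAT score) and exacerbation management in the last 12 months". Section 9.2 lists COPD exacerbations among the baseline information, and the schedule in section 9.8 marks "Exacerbation rate/symptoms/treatment" at baseline. Section 4.1 requires at least two events in the year before screening and sets no upper limit.

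The imputation model in section 14.2.5 uses the minimisation variables, group, exposure time and, if applicable, earlier responses. It does not name the prior-year count.

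**The concern.** The outcome is a count of exacerbations over a year, and a natural candidate predictor is the same patient's count over the year before. Sections 14.2.1 and 14.2.3, which state the models, do not name it. Section 14.2 could cover it, but conditionally. The text therefore supports two different covariate sets for the primary analysis: the minimisation variables alone, or those variables plus the prior count.

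Two things are at stake. The first is precision. The sample size is driven partly by between-patient overdispersion (k = 0.36 in section 14.1), and a prior count may explain some of it. Minimisation does not balance prior count, so an unadjusted model would not correct a chance imbalance in it. The second is clarity. Allocation is open to patients and sites, with only the adjudicators blinded, so it is better that the primary covariate set does not depend on a later reading of what is appropriate.

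**Working it through.** **1. Inputs (Protocol section 14.1).** Control rate 2.25 per person-year; BCG rate 1.8 (rate ratio 0.80); k = 0.36; one year of follow-up; 90% power; alpha 0.05, taken as two-sided from section 14.2; 1:1 allocation; 10% loss.

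**2. Reproducing the plan's figure.** Per-group variance term under the alternative:

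V1 = 1/2.25 + 1/1.8 + 2 × 0.36 = 0.4444 + 0.5556 + 0.72 = 1.72.

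Under the null with a pooled rate:

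V0 = 4/(2.25 + 1.8) + 0.72 = 1.7077.

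n = (1.960 × √1.7077 + 1.2816 × √1.72)² / (ln 0.8)² = 17.994 / 0.04979 = 361.4.

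This matches the stated 361, and 361/0.9 = 401.1 gives 402. Using V1 for both terms gives 363. The k of 0.36 follows from the chain in section 14.1 (SE 0.0331, 741 person-years, φ = 1.81), which contains no covariates. The stated power therefore does not rely on adjusting for prior count.

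**3. What a smaller k would do.** Power = Φ(|ln 0.8| / √(V1/361) − 1.96), with V1 = 1 + 2k. The protocol does not say how much of k the prior count explains, so the cut is assumed.

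| Assumed cut in k | k | V1 | Power at 361 per group | n per group for 90% (V1 in both terms) |
|---|---|---|---|---|
| 0% | 0.360 | 1.720 | 89.8% | 363 |
| 5% | 0.342 | 1.684 | 90.4% | 356 |
| 10% | 0.324 | 1.648 | 91.0% | 348 |
| 20% | 0.288 | 1.576 | 92.2% | 333 |
| 30% | 0.252 | 1.504 | 93.3% | 318 |

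This treats the covariate as acting only through a lower residual k at unchanged mean rates, which is an approximation.

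**4. Which cuts are plausible.** A simulation drew gamma-distributed patient rates, kept patients with at least two events in the prior year, and fitted the next year's count with and without log prior count. The cut in k was about 6% with weak year-to-year persistence, 16–22% with moderate persistence and 38–55% with almost perfect persistence. In the setting whose unadjusted k was closest to the protocol's (0.361), moderate persistence gave a residual k of 0.302, a cut of 16%. That is V1 = 1.604 and power of about 91.8%.

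A second simulation with different starting values (unadjusted k about 0.35) compared fitted standard errors of the log rate ratio. They fell from 0.0685 to 0.0673 (risk 50% stable), 0.0662 (70% stable) and 0.0637 (fully stable), so variance fell by about 4%, 7% and 14%. Full stability is a ceiling, not an expectation.

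**5. Under less favourable planning values.** At the protocol's upper dispersion of 0.65 with rate 2.25, power at 361 per group is 79.8%. A 10% cut in k gives about 82% and a 30% cut about 87%.

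**The case against.** The strongest reply is that the point is already covered. Section 14.2 sets a general rule that includes baseline values, calls what follows a brief outline and defers to the SAP. Section 14.2.1 excludes nothing. This stands to the extent that a reader might infer that the primary model deliberately omits the prior count, and the protocol does not support that. What remains is that the general rule is conditional, does not identify the prior count as the baseline value of the outcome, and is not carried into the sentences that define the models.

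A reader might also infer that the trial is biased or underpowered without this covariate. It is neither. Randomisation protects the comparison, ordinary chance imbalance is reflected in the confidence interval, and the sample size stands without the adjustment.

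A third tempting inference is that the protocol itself says exacerbation counts persist. Section 1.2.1 says only that a non-exacerbator phenotype is stable, and uses this to justify screening such patients out. It does not say that differences among patients with two or more events persist, which is what the precision gain needs.

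Finally, the baseline history and the outcome are measured differently. The questionnaire asks about "exacerbation management in the last 12 months", and the entry criterion does not specify moderate to severe events. The outcome is adjudicated and needs proof of prescription or admission (sections 8.1 and 8.2.1). A poor match would shrink the gain.

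**Conclusion.** The point holds as an unclear covariate set and a missed improvement, not as an error. Sections 14.2.1 and 14.2.3 name the minimisation variables, section 14.2 allows more, and nothing settles whether the prior-year count is included.

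The expected benefit is small: about 1 to 2 points of power at moderate persistence, within 0.6 to 3.5 points over the assumed 5–30% cut in k (90.4% or 93.3% against 89.8%). It would be less if reported history tracks the adjudicated outcome poorly. These figures rest on assumed persistence, because the protocol gives none. With a log link, adding the count leaves the meaning of the rate ratio essentially unchanged.

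**What to change.** Align sections 14.2.1 and 14.2.3 with section 14.2, in the protocol or the SAP and before outcome data are seen:

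- Name log(prior-12-month exacerbation count) as a covariate in the primary negative binomial model, in the other rate models and in the antibiotic-day and steroid-day models.
- Name baseline CAT in the CAT model.
- Include the same variables in the imputation model in section 14.2.5.

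The cost is a line or two of text and no new data collection, provided that the baseline form records the history as a number. The only statistical overhead is a simple pre-stated rule for the rare missing count, and for a zero count (where the log is undefined) in anyone found ineligible after randomisation but kept in the analysis under section 9.9. The sample size need not change.

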14.2.2 Secondary estimands

As per the primary estimand.

14.2.3 Secondary outcome estimands

Estimands for the secondary outcomes will deal with intercurrent events as per the primary estimand. All analysis models will adjust for the minimisation variables listed in Section 6.6. The differences between groups for the secondary outcomes will be presented along with 95% confidence intervals. Incidence rate outcomes (e.g. the hospitalisation rate for infective exacerbation

of airways disease at 12 months) will be analysed as per the primary outcome using negativebinomial regression models incorporating exposure time (person-years). Count outcomes (e.g. total number of days of antibiotics for AECOPD, total number of days of oral steroid therapy for AECPOD) will be analysed using Poisson regression models to calculate adjusted incidence rate ratios, unless there is compelling evidence of overdispersion, in which case negative-binomial regression models will be used. The chosen model will incorporate exposure time (person-years). The continuous secondary QOL outcome (using the CAT score) will be analysed using mixed effects linear regression models to calculate an adjusted mean difference accounting for the collection of QOL at multiple time points. Ordinal outcomes (e.g. type of exacerbation classified using two different approaches: i) a three-level classification based on Anthonisen criteria, and ii) a four-level classification based on clinical adjudication) will be analysed using mixed effect ordinal regression models to estimate the adjusted odds ratios.

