8.2 Main trial outcomes

8.2.1 Primary outcome(s)

The primary outcome is moderate to severe AECOPD rate over 12 months follow up from IMP administration date (or from the date of randomisation if no treatment was administered). This is defined by the clinical adjudication committee and will be based on an assessment of:

- basic patient details
- healthcare utilisation (taking additional antibiotics and/or steroids, as recorded in the medical record, including prescription data),
- patient-reported symptoms of the AECOPD
- laboratory results from patient-provided sputum, saliva, nose/throat swabs and DBS samples following an exacerbation

Severe events are defined by additional hospitalisation. Confirmation of events as stated in section 8.1, will occur via the CAC. Terms of reference for the CAC will be set.

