8.2.2 Secondary outcomes

We will compare the following between intervention and control groups over 12 months follow up from IMP administration date (or after the date of randomisation if no treatment was administered), unless otherwise stated.

- Hospitalisation rate for infective exacerbations equivalent to the rate of severe AECOPD.
- Quality of life (QOL), as defined by the COPD Assessment Test (CAT)

- Total number of days of antibiotic therapy for AECOPD during follow up, defined by patient self-report at each event, and confirmed by the site in the medical record (section 8.1).
- Total number of days of oral steroid therapy for AECOPD during follow up, defined by patient self-report at each event, and confirmed by the site in the medical record (section 8.1).
- Type of exacerbation (as they occur (rate over time)):
 - Defined by Anthonisen criteria, collected at AECOPD using patient self-report of symptoms. Type 1 being characterised by increased breathlessness, sputum volume and sputum purulence, type 2 by two of these three symptoms and type 3 by a single symptom.
 - Defined by the clinical adjudication committee (CAC), who will use sputum, viral and symptom data to determine aetiology of each event, categorising events as infectious (confirmed bacterial, confirmed viral, clinically likely but no organism identified) and non-infectious.

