14. STATISTICAL CONSIDERATIONS

14.1 Sample size

The sample size calculation is based on the primary outcome of moderate-severe exacerbation rate over a 12-month period. Poisson regression is often used to model count data. However, after reviewing trial and cohort studies in COPD (16, 50, 51, 52), we found that the variance of the counts of exacerbations is often greater than the mean, leading to over dispersion and hence a misspecification of the standard error under a Poisson model. A more appropriate approach, which allows for a more flexible mean-variance relationship, and which has been used to analyse COPD trials (53, 54), is to utilise a negative binomial model. We have outlined below how we have made our calculation with the expectation of using this approach.

Using the methods in Zhu and Lakkis (55), sample size calculations comparing two negative binomial rates require an estimate of the negative binomial dispersion factor. This in turn requires estimates of the following:

- 1) the standard error of the log exacerbation rate per patient per year (pp/year),
- 2) the total exposure time of study participants in the control group in person years, and
- 3) the mean rate of exacerbations pp/year.

We have estimated these parameters using data from the (theophylline with inhaled corticosteroids) TWICS trial (50) which has a similar population to our proposed study being limited to COPD patients with ≥2 exacerbations in the last 12 months. The estimates (rationale) are as follows:

- 1) 0.0331 (Mean number of acute exacerbations pp/year was reported as 2.23, with an associated 95% CI of (2.09 to 2.37). Then, SE(log(r)) = (log(2.23)-log(2.09))/1.96 = 0.0331),
- 2) 741 (Total exposure time of n=1536 patients is 1489 person years. Scaling by 772:764 ratio intervention: control gives an estimated duration, T, of 741 person years for control patients), and
- 3) 2.23 pp/year

Using equation 17 in (55), the over dispersion factor, ϕ , is estimated by $\phi=T\times r\times[SE(\log(r))]2 = 741\times2.23\times[0.0331]2 = 1.81$. Then, using equation 15 in (55), the negative binomial dispersion parameter, k, is estimated as $k = (\phi-1)/r = (1.81-1)/2.23 = 0.36$. Thus, the estimate of the negative binomial dispersion parameter we have used is 0.36.

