Our calculation has also required us to estimate the mean number of exacerbations pp/year in the control group. Again, based on a similar population studied in the TWICS trial (50), we will assume an overall mean exacerbation rate of 2.25 pp/year in the control arm (no vaccine). As noted in the 'Justification for design' section, a 20% relative reduction in the mean exacerbation rate pp/year equates to the likely MCID, is similar to other widely used therapies considered clinically meaningful to use in frequent exacerbators, and thus is an appropriate effect size upon which to base the power calculation. This reduction corresponds to an absolute decrease of 0.45 in the mean exacerbation rate pp/year from 2.25 in the control arm to 1.8 in the BCG arm. To detect this difference, comparing two negative binomial rates using the sample size formulae in (55), with 90% power, and a type 1 error rate of 5% (i.e. α =0.05), requires 361 participants per group to be randomised, or 722 participants in total. Assuming a loss to follow-up rate of 10% over a twelve-month follow-up period (see retention rate section), the study requires 402 per group to be randomised or 804 participants in total.

To allow for some uncertainty around our estimates, we have explored through sensitivity sample size calculations the impact of changing the parameters. Our proposed sample size is still likely to provide adequate power even if our estimates are not quite as expected. For example, for negative binomial dispersion parameters ranging from 0.65 to 0.3, and for mean exacerbation rates in the control arm ranging from 1.42 to 2.5, a sample size of 804 participants provides between 80% and 92% power to detect relative reductions of 20% in the mean exacerbation rate pp/year.

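### Antibiotic and steroid days: the Poisson default will not be used, and the negative-binomial fallback gives confidence intervals that are too wide

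*Protocol*

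**What the plan says.** Section 14.2.3 names total days of antibiotics and of oral steroids as count outcomes. They "will be analysed using Poisson regression models to calculate adjusted incidence rate ratios, unless there is compelling evidence of overdispersion". Where that evidence is found, the fallback is a negative binomial. Either way the model carries a person-years offset and adjusts for the minimisation variables. The section gives no threshold for what counts as compelling and names no robust or quasi-Poisson variance.

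Section 8.2.2 defines the first outcome as "Total number of days of antibiotic therapy for AECOPD during follow up, defined by patient self-report at each event", confirmed in the medical record; steroid days are defined in the same way. Section 8.2.1 bases the primary outcome partly on "healthcare utilisation (taking additional antibiotics and/or steroids, as recorded in the medical record, including prescription data"), so an event may be treated with one drug class and not the other.

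Section 14.1 reports that in earlier COPD studies the variance of exacerbation counts often exceeded the mean, "leading to over dispersion and hence a misspecification of the standard error under a Poisson model". It adopts the negative binomial for the primary outcome on that ground.

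**The concern.** Days of therapy accumulate in blocks, one course per treated exacerbation. The number of blocks is the quantity that section 14.1 finds too variable for a Poisson model, and multiplying each event by several days raises the variance-to-mean ratio further. A Poisson default for such an outcome conflicts with the protocol's own reasoning.

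The less obvious question is whether the fallback repairs this. A participant with no treated event has zero days; one with a single event jumps straight to a full course. A negative binomial fitted by maximum likelihood has one dispersion parameter to describe both the spike at zero and the spread above it. If it cannot do both, its model-based standard error will be wrong. At stake are the intervals and p-values of two named secondary outcomes, and with them the chance of recognising a real fall in antibiotic or steroid use.

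**Working it through.** **Inputs from the protocol.** Control rate: the plan will "assume an overall mean exacerbation rate of 2.25 pp/year in the control arm (no vaccine"). Effect: "from 2.25 in the control arm to 1.8 in the BCG arm", a 20% reduction. Event dispersion k = 0.36; 361 evaluable per arm; two-sided 5% (sections 14.1 and 14.2).

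**Assumptions, because the protocol is silent.** Course length c of 3 to 14 days, and a share p = 60-100% of events treated with the drug class in question.

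**1. The plan's own figures.** φ = 741 × 2.23 × 0.0331² = 1.81 and k = (1.81 − 1)/2.23 = 0.36. With a pooled null rate of 2.025, V0 = 2/2.025 + 2 × 0.36 = 1.708 and V1 = 1/2.25 + 1/1.8 + 2 × 0.36 = 1.720. Then n = [1.960√1.708 + 1.282√1.720]² / (ln 0.8)² = 361.4, and 361/0.9 = 401.1, rounded up to 402. Both stated sizes reproduce. The protocol states no standard error or power for treatment days.

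**2. Overdispersion follows from the construction.** For a fixed course c, the variance-to-mean ratio of days is c(1 + k·p·2.25):
- c = 3, p = 0.9: 3 × (1 + 0.36 × 2.025) = 5.2
- c = 7, p = 0.6: 7 × (1 + 0.36 × 1.35) = 10.4
- c = 14, p = 1: 14 × (1 + 0.36 × 2.25) = 25.3

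Simulated Pearson dispersion averaged 5 to 25 across scenarios. Its minimum over all replicates checked was 4.1, in the 3-day case.

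**3. Why the negative binomial misfits.** Take c = 7, p = 0.6, no treatment effect, and mean days 7 × 1.35 = 9.45.
- True SD of the log rate ratio: √[2(1/1.35 + 0.36)/361] = 0.078.
- Dispersion that would match the variance of days: 1/1.35 + 0.36 − 1/9.45 = 0.99.
- True share of zeros: (1 + 0.36 × 1.35)^(−1/0.36) = 33%. A negative binomial with dispersion 0.99 predicts about (1 + 0.99 × 9.45)^(−1/0.99) = 9.5%.
- Maximum likelihood raises the dispersion to reach the zeros; the simulated mean fit was 2.07. The model standard error becomes √[2(1/9.45 + 2.07)/361] = 0.110.
- 0.110/0.078 = 1.41, so the standard error is 41% too wide.

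**4. Simulation.** Event counts were drawn from a negative binomial with rate 2.25 and k = 0.36, each treated event was given a course, and models with a treatment term were fitted (361 per arm, 1,500 runs per case).

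| Courses | True SD | NB SE | Robust SE | Null rejection, NB / robust | Power at 20% reduction, NB / robust |
|---|---|---|---|---|---|
| 5-day, all events treated | 0.067 | 0.081 | 0.067 | 2.1% / 5.2% | 80% / 90% |
| 7-day, all treated | 0.068 | 0.085 | 0.067 | 1.9% / 5.3% | 77% / 91% |
| 5/7/14-day mix | 0.071 | 0.091 | 0.070 | 1.4% / 5.1% | 71% / 88% |
| 5/7-day, 60% treated | 0.080 | 0.107 | 0.079 | 1.1% / 5.1% | 49% / 77% |

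SE excess by row: 0.081/0.067 = 1.21; 0.085/0.068 = 1.25; 0.091/0.071 = 1.28; 0.107/0.080 = 1.34.

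A separate run of 500 replicates added a person-time offset with 10% of participants followed for less than the full year, a 5/7/10/14-day mix and 80% treated. Power was 55% (NB) against 78% (robust).

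**5. Range of the NB excess.**
- 3-day courses: 16%. 14-day courses with 60% treated: 56%.
- Ends of the protocol's sensitivity range, 7-day courses: 25% (k 0.3, rate 2.5) and 36% (k 0.65, rate 1.42).
- Course length varying between patients rather than between events: 7-11% in one set of runs, 16-20% in another.
- NB type I error: 0.2-3.7% across these runs; coverage with the offset 97-99%.

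**6. The alternative.** The sandwich standard error on the same log-rate model stayed within 0.96-1.05 of the true SD, with type I error 4-7% and coverage 93-96%.

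**The case against.** The strongest reply has four parts.

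*The Poisson error will not be published.* This stands. If Poisson were reported, its standard error would be 2.2 to 5.2 times too small, and the null would be rejected in 38-70% of trials. A reader might infer from this that the plan risks gross false positives. It does not: with dispersion of 4 or more in about 722 participants, any sensible reading of the rule moves to the negative binomial. For the same reason the missing threshold has little practical effect.

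*Conservative intervals are not invalid.* This also stands. A reader might conclude that neither model gives usable intervals. The negative-binomial intervals cover at or above 95%; what they lose is precision.

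*The size depends on unstated inputs, and the simulated models are simpler than the planned one.* True. Course length and treated share are assumptions, and the runs omitted the minimisation variables. Letting course length vary between patients shrinks the excess but did not remove it in any run.

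*The SAP can settle this.* In part. Section 14.2 calls itself a brief outline, and a SAP could attach a robust variance to either model without contradicting it. But the Poisson-first rule and the data-driven switch are fixed in the protocol text, at odds with section 14.1, and removing them means changing that text.

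**Conclusion.** The concern holds as a matter of efficiency and clarity. Overdispersion of treatment days is near-certain, so the Poisson default and the switch serve no purpose, and the negative-binomial model will carry the result. With model-based standard errors, its intervals on the log scale are roughly 10-55% too wide: about 20-40% for 5-7 day or mixed courses, and nearer 10-20% if course length varies mainly between patients. Type I error is about 0.2-4%. For a true 20% reduction, power is about 50-80%, against 77-92% with a robust standard error in most scenarios; over every scenario run the ranges were 39-80% and 70-92%. A real reduction in antibiotic or steroid use could therefore be reported as inconclusive.

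These figures rest on the protocol's rate, dispersion and 361 per arm, on the assumed courses and treated shares, and on model-based standard errors being used, since the protocol names no other. The outcomes are secondary, and the protocol makes no power claim for them. The primary analysis and the sample size are untouched.

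**What to change.** In section 14.2.3, specify one analysis for both day-count outcomes: a log-link Poisson mean model with the person-years offset, the minimisation variables and robust (sandwich) standard errors. Delete the overdispersion switch for these outcomes. The adjusted incidence rate ratio remains the summary measure. Carry the same sentence into the SAP.

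If the negative-binomial mean model is preferred, making it the sole model with sandwich standard errors also works: in the offset runs its robust standard error tracked the true SD (for example 0.0736 against 0.0758 with 7-day courses and 80% treated).

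The cost is one sentence in the protocol and one in the SAP, with no added data or participants. It should be done before any unblinded comparison of these outcomes.
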